### Specific Aim 1 – Association of CMR ischemic burden with clinical outcomes in the real-world

To test the hypothesis that stress CMR perfusion imaging adds predictive stratification of clinical outcomes over known risk factors for patients presenting with chest pain syndromes, at moderate pre-test risk, in a multicenter real-world setting in the US. Endpoints of interests include both primary and secondary outcomes. This aim is important because it provides the prognostic association of key CMR variables of ischemia with the observed primary and secondary events without and with adjustments to known clinical markers of patient risks, annualized event rates of primary and secondary outcomes either annualized across the entire study period or at specific intervals of study follow-up (e.g. first, second, third year of follow-up etc), net reclassification index by CMR metrics of ischemia towards current guideline-supported treatments, and potential alteration of diagnostic and therapeutic thinking.

Specific aim 1 will assess the prognostic association of presence of ischemia and percent ischemic myocardium (both by CMR) with the primary and secondary clinical outcomes. In the multi-variable analyses, key known risk markers such as patient age, patient sex, left ventricular and systolic volume (LVESV), validated pretest coronary disease probability, and validated risk score (Diamond and Forrester) will be considered for inclusion in a multivariable model, and then presence or extent of ischemia by stress CMR will be added to the model to test the null hypothesis that CMR assessment of ischemia do not add prognostic value, versus the alternative hypothesis that stress CMR assessment of ischemia do add predictive value. A significance level of 0.05 will be used. Since CMR findings will affect patient management, which in turn, will affect the clinical outcomes, in a secondary analysis, cardiac treatment (e.g. revascularization) received within 60 days of the CMR will be added to the above model to account for treatment effects on the relationship between extent of ischemia and outcome. Annualized event rates of the primary and secondary outcomes, stratified by CMR ischemia (present or absent), and CMR ischemic burden (mild, moderate, high), will be determined, both unadjusted and adjusted for cardiac treatments received. We also plan to calculate net reclassification index of these CMR metrics to event-free survival (primary and secondary outcomes).

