## Sample Size

### For sub-aim 1:

The rate of cardiac hard events (death and acute MI) is estimated based on reported evidence of 0.5% and 6% per year for patients who have absence and presence of ischemia on CMR perfusion imaging, respectively. We plan to collect follow-up events for a 4-year period after CMR. Based on prior evidence, prevalence of ischemia on CMR perfusion was 23% in referred patients.

With a sample size of 2,200 patients, 506 (23%) are assumed to be with presence of ischemia and 1694 (77%) with absence of ischemia. With incidences of 6% and 0.5% per year and a 4-year follow-up, a total of 124 of 506 patients with ischemia and 36 of 1694 patients with no ischemia are expected to experience an event, i.e. a total of 150 patients with event.

A sample size of 2,200 patients overall and 150 patients with event in a 4-year follow-up is regarded sufficient to run multivariable analysis with up to 10 variables.

With regards to the sample size considerations on the time-to-event analysis, the following settings and assumptions were used:

- Power = 80%
- Level of significance (two-sided) = 5%
- Assumed proportion in control group (i.e. no revascularization) = 77%
- Total sample size = 2,200 patients
- Number of events = 150 in total sample
- 4-year follow-up for all patients available
- The hazard ratio is estimated by a Cox proportional hazard model

With a sample size of 2,200 patients and an event rate of 124 in group 1 and 36 in group 2, a hazard ratio of 0.59 can be detected with the above mentioned settings and assumptions (i.e. 41% risk reduction rate).

For sub-aim 2.3 (comparison to the historical FAME 2 study

As reported in published data (own BWH dataset and [name] et al Circulation 2011 Apr 12;123(14):1509-18), the event rate of patients who underwent revascularization guided by CMR ischemia (i.e. CMR physiologic guidance) is about 5% per year, i.e. 10% in a 2-year follow-up. In the

historic fame-2 study, the 2-year event rate of patients who did not use physiological guidance (N=441), was 19.5%. With a power of 80%, a two-sided alpha of 5% and an assumed difference under H1 of -9.5%, the sample size of patients in this registry needs to be at least 180 patients.

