## **Statistical Analyses**

### **Specific aim 1**

Unadjusted and multivariable survival analyses associating presence of ischemia and percent ischemic myocardium (both by CMR), with the primary and secondary clinical outcomes will be performed. In the multi-variable analyses, key known risk markers such as age, patient sex, left ventricular and systolic volume (LVESV), validated pretest coronary disease probability, and validated risk score (Diamond and Forrester) will be modeled, and then extent of ischemia by stress CMR studies will be added to the model to test the null hypothesis that CMR findings do not add predictive value, versus the alternative hypothesis that stress CMR findings do add predictive value. A significance level of 0.05 will be used. Since CMR findings will affect patient management, which in turn, will affect the clinical outcomes, in a secondary analysis, cardiac treatment (e.g. revascularization) received within 60 days of the CMR will be added to the above model to account for treatment effects on the relationship between extent of ischemia and outcome. Annualized event rates of the primary and secondary outcomes, stratified by CMR ischemia (present or absent), and CMR ischemic burden (mild, moderate, high), will be determined, both unadjusted and adjusted for cardiac treatments received. We also plan to calculate net reclassification index of these CMR metrics to event-free survival (primary and secondary outcomes). In addition, we will examine the annual event rates of primary and secondary outcomes in each of these subgroups and perform corresponding comparative analyses.

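### The net reclassification index is planned without optimism correction and would overstate reclassification where the ischemia metric is only weakly prognostic

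*Combined protocol and SAP*

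**What the plan says.** Under Statistical Analyses, Specific aim 1, the index is specified in one sentence: "We also plan to calculate net reclassification index of these CMR metrics to event-free survival (primary and secondary outcomes". The metrics are ischemia (present or absent) and its extent, with burden also graded in levels. The same sentence closes the section Specific Aim 1 – Association of CMR ischemic burden with clinical outcomes, whose opening paragraph also lists a "net reclassification index by CMR metrics of ischemia towards current guideline-supported treatments".

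Neither section says whether the index is category-free or category-based. Neither gives risk cut-offs, a time horizon or an interval method. The formal test of added value is separate: a base model of clinical markers is compared with the same model plus the CMR metric, at 0.05.

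Sample Size, For sub-aim 1, supplies the scale: "Total sample size = 2,200 patients" and "Number of events = 150 in total sample". That number "is regarded sufficient to run multivariable analysis with up to 10 variables". The expected effect is large, with annual event rates of "0.5% and 6% per year for patients who have absence and presence of ischemia on CMR perfusion imaging, respectively".

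**The concern.** When one data set both fits two nested models and scores the change between them, the added coefficient has already been tuned to the events on which it is judged. The resulting apparent index is too high on average. The excess is largest when the true effect is small, when the metric uses several parameters (burden levels), and when events are few. If clinical markers are also selected from the data, which the Aim 1 wording allows, that selection can add further optimism.

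What is at stake is the reported amount of reclassification. The nested-model test guards the statement that CMR adds information; it does not guard the size of the index. The Rationale section expects the aims to inform insurers' coverage decisions. It does not name the index, but an inflated figure in an Aim 1 publication would be available for that use.

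**Working it through.** **1. The plan's own figure.** The documents state no value for the index, so the cohort set-up was checked through the detectable hazard ratio of 0.59. With 23% in one group, 80% power and two-sided 5%:

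d = (1.960 + 0.842)² / [0.23 × 0.77 × (ln 0.59)²] = 7.85 / (0.1771 × 0.2784) = 159.2, so 160 events.

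This matches 124 + 36 = 160, not the listed 150. At 150 events, |ln HR| = √[7.85 / (0.1771 × 150)] = 0.544, giving HR 0.581, and power at 0.59 is 77.6%. The mismatch should be tidied, but it does not materially change what follows; both event counts were used.

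**2. The effect the plan assumes.** "With a sample size of 2,200 patients and an event rate of 124 in group 1 and 36 in group 2" gives odds of 124/382 = 0.325 and 36/1,658 = 0.0217, so an odds ratio of about 15.

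**3. The index.** NRI = [P(up | event) − P(down | event)] + [P(down | non-event) − P(up | non-event)], where up and down refer to predicted risk after the marker is added.

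**4. Uninformative marker.** From the documents: N = 2,200, about 150 or 160 events, 4 years, five named base markers (nine also tried) and 23% with ischemia. Assumed: normal covariates, SD of the true linear predictor 0.4 or 0.8, the risk cut-offs, and correlation of the marker with baseline risk of 0 or 0.4. Logistic models used 1,500 cohorts per setting; Cox models used 400, so the simulation error on a share near 50% is about √(0.25/400) = 2.5 points.

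| Index and marker | Cohorts with a positive same-sample index |
|---|---|
| Category-free, binary, independent of risk | 91-97% (mean about 0.055) |
| Category-free, four-level burden, independent | 94-97% (mean 0.083-0.092) |
| Category-free, extent, independent | 80-86% |
| Category-free, continuous, independent | 75-81% |
| Category-free, correlation 0.4: binary / extent / continuous | 63-65% / 58-59% / 76-80% |
| Category-based, one added term | 49-61% (mean below 0.01) |
| Category-based, four-level burden | 61-82% |

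The single-term Cox models scored in a fresh cohort of 2,200 gave a positive category-free index in about 47-56% of cohorts, with a mean of −0.01 to 0.02. With cut-offs of 5% and 10% the share was about 41-50%. Scoring new patients removes the bias.

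**5. Modest effect (assumed odds ratio 1.5, burden levels), two separate runs.**
- Category-free: 0.162 apparent v 0.123 in new patients (ratio 1.32), and 0.178 v 0.132 (ratio 1.35).
- Assumed cut-offs of 4% and 12%: 0.036 v 0.016 (ratio 2.25), and 0.040 v 0.024 (ratio 1.67).

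**6. Strong effect.** At an odds ratio of 3: 0.452 v 0.447. At the sub-aim 1 rates: 1.155 v 1.151 (binary) and 1.165 v 1.151 (burden levels), an excess of 0.014/1.151 = 1.2% at most.

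**The case against.** Several points on the other side stand.

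- **The planned effect is strong.** At an odds ratio of about 15 the correction changes almost nothing. The weaker-effect results rest on an assumed odds ratio; the documents give no effect size for secondary outcomes.
- **The event count is for another endpoint.** The 150 events are deaths and MIs. The primary outcome adds late revascularization, so it should have more events and less optimism.
- **The index is supplementary.** It has no success criterion. A positive sign is also not a significant result: with independent null markers the category-free index exceeded z = 1.96 (simple variance) in about 4-8% of cohorts. For binary or extent markers correlated 0.4 with risk, however, this rose to about 27-30%.
- **Same-sample calculation is inferred.** The documents are silent on it; nothing states it.

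Two stronger readings are tempting. A reader might infer that any uninformative marker would look positive in about 94% of cohorts of this size. That figure belongs to a category-free index with a binary or multi-level marker independent of the base covariates. The plan specifies neither, and across the definitions it leaves open the share runs from about 49% to 97%. A reader might also infer from the phrase on guideline-supported treatments that reclassification is judged against treatment decisions. The phrase can equally mean guideline thresholds used as risk categories, and both Aim 1 sections give event-free survival as the reference.

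What does not stand is that this is only missing detail. Bootstrap correction is a better method than the apparent index, and the same data can supply it.

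**Conclusion.** The concern holds in limited form. The plan provides no optimism correction for the index and does not define it. If it is computed in the fitting sample, it overstates reclassification for weak markers. At an assumed odds ratio of 1.5 with burden levels, the overstatement is about a third on the category-free scale and about 1.7 to 2.3 times with the assumed three categories. At the effect planned for death or MI it is about 1% or less.

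The correction therefore matters mainly for burden levels and for secondary outcomes with modest effects. The documents do not support the inference that the Aim 1 conclusion on added value is itself compromised, since that rests on the nested-model test. The sizes depend on the simulated covariate structure, cut-offs, correlation and odds ratio, none of which the documents give. The direction of the bias and its disappearance in new patients do not depend on one particular choice among them.

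**What to change.** In Statistical Analyses, Specific aim 1, state that:

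- the index is evaluated at 4 years, with its type named and its risk categories fixed before analysis;
- it is reported with bootstrap optimism correction. In each resample all model building is repeated, including any selection of base markers, and the index is computed in the resample and again in the full cohort using the resample's models. The mean difference is subtracted from the apparent index;
- event and non-event parts are shown separately, for each CMR metric and each outcome.

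In the Specific Aim 1 description, state that observed events are the reference and that guideline thresholds, if used, only define the categories.

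The cost is a few sentences in the plan and a few hours of programming, with no new data. The downside is a slightly less favourable reported index where effects are modest.

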### **Interim analysis at the end of the 2-year study period**

The study investigators agree with collaborators from Siemens and Bayer that an interim analysis at the end of the 2-year study period, of the proposed N=2,200, will inform the magnitude of the risk reduction rate. In addition, it will provide reasonable guidance to what actions will be appropriate, if necessary, to further evaluate specific aim 1. These actions include the possibility of proposing another study aiming at a larger sample size.

### **Specific aim 2 (2 separate analyses for sub-aims 2.1 and 2.2, respectively)**

We structured the present study's analysis of observational data to mimic a randomized clinical trial: a patient's assignment to a treatment was based on the therapy selected in the first 60 days after stress CMR perfusion study and nonrandomized treatment adjusted for via a propensity score. This time point of 60 days was selected from previous work indicating that revascularization performed within this timeframe resulted from the noninvasive imaging study, whereas referrals after 60 days tended to be attributable to worsening clinical status. Based on our pilot data, approximately 10-15% of patients undergo early coronary revascularization within the first 60 days after CMR. We therefore anticipate that 85-90% of the study cohort received MED whereas 10-15% received INT.

We plan to examine the assumptions of proportional hazards in each of the Cox models. In addition, performance of the propensity score model will be tested by comparing the prognostic associations between treatment and clinical outcomes, without and with that propensity score matching. Key risk markers will be compared between the treatment groups, without and with inclusion of the propensity score matching.

**Step 1: Propensity Score to Treatment** We plan to structure the study analysis of observational data in SA1 to mimic a randomized clinical trial: a) assignment of coronary intervention (INT) vs. medical therapy (MED) is based on the therapy selected in the initial 60 days after imaging and b) nonrandomized treatment adjusted for via a propensity score. Either PCI or CABG will define coronary revascularization. Follow-up time begins at the time of the index stress CMR imaging. To adjust for non-randomization of treatment, a single propensity score will be developed using logistic regression to model the decision to refer to revascularization considering all factors known to influence the referral decision. This single composite propensity score represents the probability of treatment assignment, which will be included in all subsequent survival models (step 2) associating stress CMR perfusion guided-treatment with the respective endpoints in each of the 3 sub-aims. This adjustment reduces the bias introduced by nonrandomized referral to INT in practice. While all factors known to influence this referral decision will be considered for entry into this logistic regression model, based on existing literature, the most likely predictors of referral to INT include % ischemic myocardium (% myocardial mass based on number of segments, by CMR), typical angina symptoms (yes if positive response to 2 of 3 Diamond and Forrester qualities, else no), infarct size (LGE size, grams of myocardial mass), ischemic ST changes on rest ECG (yes/no), pre-test coronary disease probability (ordinal), and prior cardiac catheterization (yes/no). We anticipate that 10-15% of patients (~n=300) received INT so model over-fitting will not occur when constructing this logistic regression model.

**Step 2: Multivariable survival analyses for treatment's impact incorporating the propensity score (sub-aims 2.1 and 2.2).** A Cox proportional hazards model will be used to assess the association of treatment with the primary outcome (sub-aim 2.1) and secondary outcome-free survival (sub-aim 2.2). For each of sub-aim 2.1 and 2.2, we plan to build a survival model using Cox proportional hazards regression to control for the effects of baseline patient differences. Key known risk markers to be included in these models are age, sex, diabetes, and % ischemic myocardium. Major Treatment (INT or MED) and the propensity score will then be entered into the model to assess for any survival advantage from INT vs MED adjusting for the nonrandomized referral pattern. Any potential impact by any covariate in the model onto the survival benefit from INT, will be tested by adding an interaction term between treatment and the covariate of interest.

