## Study Endpoints and Hypotheses to Test

### Study Endpoints

Primary outcomes include all-cause mortality, acute myocardial infarction (AMI), and late coronary revascularization (PCI or CABG beyond 60 days after CMR).

Secondary outcomes include non-fatal cardiac events (including cardiac hospitalizations for unstable angina or heart failure, heart transplant, significant ventricular arrhythmias, and strokes), alteration of diagnostic and therapeutic decision, and cardiac event-weighted QALY.

The specific aims of this project are listed below:

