### **Specific Aim 2 – Assessment of the impact of CMR-guided invasive coronary revascularization, compared with medical therapy, on primary outcomes**

Sub-aim 2.1 Using a propensity score-matching analysis, test the hypothesis that in real-world clinical practice that stress CMR perfusion imaging-guided use of invasive coronary revascularization (INT) (defined by INT performed within 60 days after CMR) offers *AMI-free, coronary revascularization-free, survival benefits* over medical therapy (MED) in patients with suspected ischemia. We will estimate the # lives saved per 100 patients treated with INT versus MED (based on predicted primary outcome rate amongst MED)–(predicted primary outcome rate amongst INT)

Sub-aim 2.2 Using a propensity score-matching analysis, test the hypothesis that in real-world clinical practice that stress CMR perfusion imaging-guided use of INT offers *survival benefits free of primary or secondary outcomes* over MED in patients with suspected ischemia.

Sub-aim 2.3 The preferred initial treatment for patients with stable ischemic heart disease (SIHD) is the best available medical therapy. The benefits of using physiologic ischemia-based guidance to performing INT has been shown in the FAME and FAME-2 trials where fraction-flow-reserve was used to assess physiological significance of coronary stenosis. In FAME (multi-vessel SIHD) and FAME 2 (single or multi-vessel SIHD) trials: a 29% and 66% relative risk reduction of primary outcome at 2-years were reported, respectively. CMR perfusion assessment had demonstrated remarkable correlation to FFR based assessment of coronary physiologic significance. For sub-aim 2.3, test the hypothesis that comparing to the FAME-2 primary outcome rate of patients managed by medical management alone, CMR-guided INT patients have a relative risk reduction of 2-year primary outcomes  $\geq 30\%$ .

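### Sub-aims 2.1 and 2.2 set INT or MED by procedures in days 0-60 but start the clock at the CMR, so a few early events fall in the wrong group; the bias is small at the plan's rates and can go either way

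*Combined protocol and SAP*

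**What the plan says.** - **Group.** Specific Aim 2, sub-aim 2.1, has INT "defined by INT performed within 60 days after CMR". Statistical Analyses, Specific aim 2, words it differently: "assignment to a treatment was based on the therapy selected in the first 60 days after stress CMR perfusion study" in the introduction and "assignment of coronary intervention (INT) vs. medical therapy (MED) is based on the therapy selected in the initial 60 days after imaging" in Step 1.
- **Clock.** Step 1: "Follow-up time begins at the time of the index stress CMR imaging".
- **Model.** Step 2: "Major Treatment (INT or MED) and the propensity score will then be entered into the model". No landmark, delayed entry or time-dependent term is stated, and there is no rule for events between the CMR and the procedure.
- **Reason for the window.** The introduction to Specific aim 2 cites previous work that "revascularization performed within this timeframe resulted from the noninvasive imaging study".
- **Outcome.** Under Study Endpoints, death and AMI carry no starting day, so they count from the CMR. Revascularization counts only as "late coronary revascularization (PCI or CABG beyond 60 days after CMR").
- **Diagnostics.** "We plan to examine the assumptions of proportional hazards in each of the Cox models".

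**The concern.** The group is fixed by something that happens after time zero. Most day 0-60 events are still classified correctly: those after an early procedure, and those in patients who never have one. Two kinds are not.

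1. A patient due for revascularization who dies first never has the procedure and is counted as MED. This favours INT.
2. A patient with no procedure planned who has an AMI and then PCI or CABG by day 60 is counted as INT, with an event that preceded treatment. This favours MED. In sub-aim 2.2 an unstable angina admission acts in the same way. The plan attributes procedures in the window to the imaging, so it does not separate this case.

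A propensity score built on baseline referral factors cannot repair grouping by later events. At stake is the hazard ratio by which sub-aims 2.1 and 2.2 judge whether INT is better than MED. As written, a reader could not tell which way it had been shifted.

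**Working it through.** **The plan's own figure.** The plan gives no figure for this bias. Its only treatment hazard ratio is 0.59 (Sample Size, for sub-aim 1). With 124 + 36 = 160 events and a 23/77 split: exp(-(1.960 + 0.842)/√(160 × 0.23 × 0.77)) = exp(-0.526) = 0.59, which reproduces. (The section also states 150 events, which would give 0.58; that is a separate matter.)

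**Inputs from the documents.** 506 patients with ischemia at 6% per year; 1,694 without at 0.5% per year; 4 years of follow-up; about 300 INT (Step 1).

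**Assumptions, not in the documents.** Procedures uniform over days 0-60 (mean wait 30 days); the 300 INT patients drawn from those with ischemia; constant hazard; various death/AMI splits; and various shares of early AMIs, in patients with no planned procedure, that lead to PCI or CABG by day 60. A patient with a planned procedure who has a non-fatal AMI is taken to have it anyway.

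**Events in days 0-60** (60/365.25 = 0.164 years):
- With ischemia: 506 × (1 - exp(-0.06 × 0.164)) = 5.0
- Without: 1,694 × (1 - exp(-0.005 × 0.164)) = 1.4
- Total about 6.4, against 506 × (1 - exp(-0.24)) + 1,694 × (1 - exp(-0.02)) = 108.0 + 33.5 = 141.5 over 4 years.

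**Events open to misassignment:**
- Before a planned procedure: 300 × 30/365.25 = 24.6 person-years; × 0.06 = 1.48 events.
- In patients with no planned procedure: 206 × 0.0098 + 1.4 = 3.4 events.

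| Assumed deaths among events | Early AMIs leading to a procedure | Deaths moved to MED | AMIs moved to INT | Null HR (simulated) |
|---|---|---|---|---|
| 100% | none | 1.48 | 0 | 0.95 |
| 50% | half | 0.74 | 3.4 × 0.5 × 0.5 = 0.85 | 1.00 |
| 25% | all | 0.37 | 3.4 × 0.75 = 2.6 | 1.09 |

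So about 1 to 3 events change group, relative to what was planned at the CMR. In the last row, a further 1.48 × 0.75 = 1.1 AMIs occur in patients awaiting a planned procedure and are counted under INT.

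**Hazard ratios.** These come from large simulations of a Cox model with a binary treatment, stratified by ischemia.
- No true effect: 0.95-1.09 for death/AMI; about 0.96-1.06 once late revascularization is added at an assumed 3-6% per year in ischemic patients. Late revascularization cannot occur before day 60, so it only dilutes the shift.
- True HR 0.70: about 0.66-0.77 for death/AMI only; about 0.67-0.75 with late revascularization.
- With no added periprocedural risk, a day-60 landmark and a time-dependent treatment term each give a null HR of about 1.00.

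**Against sampling error.** For death/AMI, SE(log HR) ≈ 1/√(108 × 0.593 × 0.407) = 0.20, where 0.593 = 300/506. With 6% per year late revascularization there are about 190 first events in ischemic patients, and 1/√(190 × 0.593 × 0.407) = 0.15. The largest null shift, ln 1.09 = 0.086, is 0.43 of a standard error of 0.20. The largest at HR 0.70, ln(0.77/0.70) = 0.095, is just under half of one.

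**Would the planned diagnostic catch it?** In simulation at constant hazard, the proportional-hazards test rejected in 6-8% (rank time) or 9-16% (log time) of trials, against 5% by chance. Usually it would not.

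**Sensitivity only.** If the first-60-day hazard were 3 or 5 times higher, the death/AMI null HR would range over 0.86-1.27 or 0.79-1.45. Nothing in the documents supports those multiples.

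Sub-aim 2.2 is not quantified, because the documents give no secondary-event rates.

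**The case against.** The strongest reply is that the effect is close to nil at the plan's own rates: a handful of events, two errors of opposite sign that can cancel, and a shift below half a standard error. That stands, and it limits the severity. The simulated model also has no propensity score, matching or covariates, so its standard errors apply only approximately to the planned analysis.

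A second reply is that therapy *selected* in the Statistical Analyses means the decision, not the procedure, so a patient who dies while waiting would still be INT. This does not rescue the plan. Sub-aim 2.1 says *performed*, Step 1 lets PCI or CABG define revascularization, and the outcome form in Appendix A4 dates procedures. A form section for diagnostic and therapeutic decisions is listed in the appendix, but no dated decision field is shown. At best the wording is inconsistent.

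A reader might infer something stronger: that this is the familiar immortal-time bias, that it systematically flatters INT, and that it could by itself produce a false finding of benefit. The documents do not support that. The second error runs the other way, and at the plan's rates the net shift is small. Large shifts appear only with an early hazard several times higher, which is an assumption.

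**Conclusion.** The concern holds in a limited form. As written, the model misassigns some day 0-60 events, and neither the propensity score nor the proportional-hazards check deals with this. At the plan's constant rates the bias is small against sampling error. Its sign depends on the death/AMI split and on how many early AMIs lead to a procedure, and the documents give neither. The ranges rest on those assumptions, on the assumed procedure timing and INT allocation, and on the assumed late revascularization rates. Severity is minor to moderate: it would not overturn the study, but it is avoidable with data already being collected.

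**What to change.** In Specific aim 2, Steps 1 and 2:

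1. **Primary model.** Keep follow-up from the CMR. Code INT as a time-dependent covariate that switches from MED to INT at a PCI or CABG on or before day 60, with the propensity score as a covariate as in Step 2. Earlier events then count under MED, and periprocedural events are kept under INT. State a rule for events dated the same day as the procedure, since Appendix A4 shows dates without clock times for these events.
2. **Prespecified sensitivity analysis.** A day-60 landmark: patients event-free at day 60 (for 2.2, also free of secondary events), grouped by INT status at that day, propensity score matched in that set, clock from day 60. State that the result applies only to those patients.
3. **Table.** Day 0-60 deaths, AMIs and secondary events by group, and by whether they came before or after the procedure.
4. **Wording.** Reconcile *performed* in sub-aim 2.1 with therapy *selected* in the Statistical Analyses.

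The landmark should not be primary because it drops about 6 events, including periprocedural ones, which favours INT. With an assumed 1% periprocedural death/AMI risk and no other effect, the time-dependent model shows an HR of about 1.09 and the landmark 1.00-1.01.

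**Cost.** SAP wording and modest programming. Event times (Data to Collect, Clinical Outcomes) and procedure dates (Appendix A4) are already collected. The time-dependent model fits the matching named in Specific Aim 2 less easily, and a baseline score does not adjust for clinical worsening between the CMR and the procedure.
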